After 4 weeks  $\pm$  2 days from Visit 2, during the assessment period patients receiving the extemporaneous combination of ZOF 30 mg and AML 5 mg, will be further evaluated (Visit 3): controlled patients (sitting SBP/DBP  $\leq$ 130/80 mmHg) will continue the same extemporaneous combination for additional 4 weeks  $\pm$  2 days, while uncontrolled patients (sitting SBP/DBP >130/80 mmHg) will be up-titrated from ZOF/AML 30/5 mg to ZOF/AML 30/10 mg for further 4 weeks  $\pm$  2 days.

At Visit 3 patients with SBP/DBP values classified as Grade 3 (SBP  $\geq$  180 or DBP  $\geq$  110 mmHg) hypertension will be withdrawn from the study.

If patients at Visit 3, do not tolerate the extemporaneous combination treatment or they have an adherence range below 80% or superior to 120%, they will be withdrawn from the study. At the end of the assessment period (8 weeks  $\pm$  4 days) at Visit 4, the anti-hypertensive effect of the extemporaneous combination (ZOF/AML 30/5 mg and ZOF/AML 30/10 mg) will be evaluated.

Efforts will be made to achieve 1:1 ratio in the enrolment of patients receiving any ACE-i or allowed CCBs. At Visit 2, a minimum of 45% of uncontrolled patients receiving treatment with ZOF 30 mg or AML 5 mg are required to enter the assessment period, in order to maintain a balance between the 2 treatments during the assessment period.

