### 6.5 Prior and Concomitant Medications

Prior and concomitant medications will be coded using the World Health Organization Drug Dictionary (WHO-DD) version Sep 2021 or later. Concomitant procedures will be coded using MedDRA version 24.1 or later.

Prior medication is defined as any medication taken within 30 days prior to the start of the study which has a stop date prior to the date of first dose of monotherapy (ZOF 30 mg or AML 5 mg). Concomitant medication is defined as any medication with a start date on or before the date of *last* dose of study drug and is ongoing or has a stop date on or after date of *first* dose of monotherapy (ZOF 30 mg or AML 5 mg).

Prior and concomitant medications will be summarized separately by Anatomic Therapeutic Class (ATC) Level 1 and Preferred Term by combined treatment group (ZOF/AML 30/5 mg or ZOF/AML 30/10 mg) and All Patients for the SAF population. That is, all patients in the SAF population who took at least one prior/concomitant medication will be summarized together in the All Patients column of the corresponding summary tables. All patients who take ZOF/AML 30/10 mg will be summarized in the ZOF/AML 30/10 mg column, even for medications they took in the monotherapy period or while taking the ZOF/AML 30/5 mg regimen. Lastly, all patients who take ZOF/AML 30/5 mg for the duration of the combined therapy period will be summarized in the ZOF/AML 30/5 mg column, even for medications they took in the monotherapy period.

Patients taking the same medication multiple times will be counted once per medication. Prior and concomitant medications as well as concomitant procedures will be presented in by-patient data listings for the SAF population.

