### 8.2 Adverse Events, Adverse Drug Reactions, and Deaths

Adverse Events (AEs) are any untoward medical occurrence in a clinical trial patient administered a medicinal product and which does not necessarily have a causal relationship with this treatment.

*Treatment Emergent AEs (TEAEs)* are defined as AEs that occur only once treatment has started (after the first dose of monotherapy of ZOF or AML). Thus, all AEs that occur in both the monotherapy and combined therapy periods will be considered treatment-emergent.

Adverse Drug Reactions (ADRs) are defined as AEs that have a relationship of "certain," "probable," "possible," or "unassessable."

All AEs will be coded using the Medical Dictionary for Regulatory Activities (MedDRA) version 24.1 or later.

The following tabulations will be produced for the monotherapy period and the combination therapy periods for the SAF population:

- Monotherapy Period (Day of Visit 1 through day before Day of Visit 2)
  - All treatment-emergent AEs (TEAEs)

- Severe TEAEs
- Adverse Drug Reactions (ADRs)
- TEAEs leading to study discontinuation
- Serious TEAEs (TESAEs)
- o Serious ADRs
- TESAEs with outcome of death
- Combination Therapy Period (Day of Visit 2 through Day of Visit 4)
  - All treatment-emergent AEs (TEAEs)
  - Severe TEAEs
  - Adverse Drug Reactions (ADRs)
  - TEAEs leading to study discontinuation
  - Serious TEAEs (TESAEs)
  - Serious ADRs
  - TESAEs with outcome of death

Key guidelines for counting incidence proportions of AEs/TEAEs/ADRs (collectively referred to as AEs for the remainder of this section) are as follows:

- When a patient has the same AE reported multiple times during an analysis period based on MedDRA terminology (SOC or PT), the patient will only be counted once within a level of MedDRA in an AE incidence table.
- When assessing investigator reported relationship to study drug of the AEs, if an AE reported multiple times changes in causal relationship during an analysis period for a patient, the event with highest relatedness will be presented. Related AEs (i.e., ADRs) will include those reported as "certain," "probable," "possible," or "unassessable" by the investigator.

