- When summarizing severity of the AEs (mild, moderate, severe), if there are multiple AEs of the same preferred term but different severity during an analysis period for a patient, the AE with the maximum severity will be reported. If the AE term (SOC and PT) is reported more than once, one of them with missing severity, and at least another with non-missing severity, the maximum severity will be chosen from the non-missing severity and the missing severity can be ignored. If all are of missing severity, then the AE severity will be summarized with an additional "Missing" category. In summary of severe AEs, missing severity will be included in severe category following the conservative approach.

All AE tabulations for the monotherapy period will present the incidences separately for the monotherapy groups (ZOF 30 mg or AML 5 mg) and All Patients for the SAF population. That is, all patients who experienced at least one AE in the monotherapy period will be summarized together in the All Patients column of the corresponding summary tables. All patients who take ZOF 30 mg will be summarized in the ZOF 30 mg column and all patients who take AML 5 mg will be summarized in the AML 5 mg column.

All AE tabulations for the combined therapy period will present the incidences separately for the combined treatment groups (ZOF/AML 30/5 mg or ZOF/AML 30/10 mg) and All Patients for the SAF population. That is, all patients who experienced at least one AE in the combined therapy period will be summarized together in the All Patients column of the corresponding summary tables. All patients who take ZOF/AML 30/10 mg will be summarized in the ZOF/AML 30/10 mg column, even for AEs that occurred while taking the ZOF/AML 30/5 regimen. Lastly, all patients who take ZOF/AML 30/5 mg for the duration of the combined therapy period will be summarized in the ZOF/AML 5 mg column.

In summaries by SOC and PT (for both monotherapy and combined therapy periods), AEs will be sorted by descending frequency for SOC and PT in the All Patients column. All AEs will also be presented in bypatient data listings for Adverse Events for the SAF population.

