## Table 14.3.1.2.1 Summary of Treatment Emergent Adverse Events by System Organ Class and Preferred Term – Monotherapy Period (Safety Population)

Adverse Events [1,2,3,4]	Statistic	ZOF 30 mg (N=xx)	AML 5 mg (N=xx)	All Patients (N=xx)
Total Number of TEAEs	n	XX	XX	xx
Number of Patients with at Least One TEAE	n (%)	xx (xx.x)	xx (xx.x)	xx (xx.x)
System Organ Class #1	n (%)	xx (xx.x)	xx (xx.x)	xx (xx.x)
Preferred Term #1	n (%)	xx (xx.x)	xx (xx.x)	xx (xx.x)
Preferred Term #2	n (%)	xx (xx.x)	xx (xx.x)	xx (xx.x)
Preferred Term #3	n (%)	xx (xx.x)	xx (xx.x)	xx (xx.x)
etc.				
System Organ Class #2	n (%)	xx (xx.x)	xx (xx.x)	xx (xx.x)
Preferred Term #1	n (%)	xx (xx.x)	xx (xx.x)	xx (xx.x)
Preferred Term #2	n (%)	xx (xx.x)	xx (xx.x)	xx (xx.x)
Preferred Term #3	n (%)	xx (xx.x)	xx (xx.x)	xx (xx.x)
etc.				

[1] AE: Adverse Event. Defined as any untoward medical occurrence in a clinical trial patient administered a medicinal product and which does not necessarily have a causal relationship with this treatment.

[2] TEAE: Treatment Emergent Adverse Event. Defined as AEs that occur after the first dose of monotherapy of ZOF or AML.

[3] Patients will be counted once per System Organ Class/Preferred Term (SOC/PT).

[4] MedDRA Dictionary version XX.X was used to code adverse events.

Source: Listings 16.2.7.1, 16.2.7.2, 16.2.7.3

Program Name: XXXX.SAS

Date: DDMMMYYYY

- For the combined therapy period tables presented in the list below: Patients will be classified as either ZOF/AML 30/5 mg or ZOF/AML 30/10 mg such that no patients are counted in both groups. That is, even though patients in the ZOF/AML 30/10 mg group are also exposed to the ZOF/AML 30/5 mg treatment, they will only be included in the ZOF/AML 30/10 mg and All Patients columns, not within the ZOF/AML 30/5 mg column. Patients that do not belong to the ZOF/AML 30/5 mg or ZOF/AML 30/10 mg group will be included only in the All Patients column.
- Repeat for the following tables:
  - 14.3.1.2.2 Summary of Treatment Emergent Adverse Events by System Organ Class and Preferred Term Combined Therapy Period Safety Population
     In the column headers, "ZOF 30 mg" and "AML 5mg" will change to "ZOF/AML 30/5 mg [4]" and "ZOF/AML 30/10 mg [4]", respectively.
  - 14.3.1.3.1 Summary of Treatment Emergent Severe Adverse Events by System Organ Class and Preferred Term Monotherapy Period Safety Population
    - Rows 1 and 2 will change from TEAE(s) to Severe TEAE(s).

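### Read literally, SAP 8.2 leaves patients who stop early on ZOF/AML 30/5 mg out of both dose columns of the combined-period AE tables, and the disposition shell implies a different rule

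*SAP*

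**What the plan says.** SAP 8.2 tabulates adverse events for a monotherapy period and for a second period headed "Combination Therapy Period (Day of Visit 2 through Day of Visit 4". One of the tabulations for the second period is "TEAEs leading to study discontinuation".

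Two rules decide which dose column a patient enters:

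- For the higher dose: "All patients who take ZOF/AML 30/10 mg will be summarized in the ZOF/AML 30/10 mg column, even for AEs that occurred while taking" the lower dose. No completion or duration is required.
- For the lower dose: "all patients who take ZOF/AML 30/5 mg for the duration of the combined therapy period will be summarized in the ZOF/AML 5 mg column". The label in that sentence drops the zofenopril strength; the shells call the column ZOF/AML 30/5 mg.

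SAP 6.5 uses the same condition for the prior and concomitant medication tables: "all patients who take ZOF/AML 30/5 mg for the duration of the combined therapy period will be summarized in the ZOF/AML 30/5 mg column".

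The programming notes under the AE shells (Tables 14.3.1.1.1 and 14.3.1.2.1) then say: "Patients that do not belong to the ZOF/AML 30/5 mg or ZOF/AML 30/10 mg group will be included only in the All Patients column".

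SAP 5.5 gives the general rule, that a patient is classed under one combination or the other and never both. It sets no duration condition and does not say where someone who stops early on 30/5 mg belongs. SAP 8 applies 5.5 to the safety results unless something else is specified.

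**The concern.** Everyone who receives the combination starts on 30/5 mg, so every stop between Visit 2 and Visit 3 happens on that regimen. The plan foresees such stops. In SAP 4.1, "If patients at Visit 3, do not tolerate the extemporaneous combination treatment" is a ground for withdrawal, and Protocol sections 5 and 10 agree.

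Under the wording of 8.2 these patients did not take 30/5 mg through Visit 4, and they never took 30/10 mg, so they enter neither dose column. The lower-dose column then holds completers only, while the higher-dose column holds completers and drop-outs. The effect is most direct in Table 14.3.1.5.2 (discontinuation TEAEs). It also removes early stoppers from the 30/5 mg columns for severe TEAEs, ADRs, serious TEAEs, serious ADRs and deaths. Endpoint 2.5 concerns safety and tolerability of the combination with either amlodipine dose, and these columns are its only tabular split of AEs by dose.

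**Working it through.** The plan gives no figure for this point, so there is none to reproduce. The check has two parts.

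**1. Trace each pathway after Visit 2.** The middle column applies SAP 8.2 and the shell notes as written. The last column puts everyone who took 30/5 mg and was never up-titrated under 30/5 mg.

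| Pathway | SAP 8.2 as written | Never up-titrated rule |
|---|---|---|
| Stops on 30/5 mg between Visits 2 and 3 | All Patients only | 30/5 mg |
| Withdrawn at Visit 3, not tolerating 30/5 mg | All Patients only | 30/5 mg |
| Controlled at Visit 3, stops on 30/5 mg before Visit 4 | All Patients only | 30/5 mg |
| Controlled at Visit 3, completes on 30/5 mg | 30/5 mg | 30/5 mg |
| Up-titrated, stops before Visit 4 | 30/10 mg | 30/10 mg |
| Up-titrated, completes | 30/10 mg | 30/10 mg |

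As written, no pathway with premature discontinuation reaches the 30/5 mg column. The only exceptions would be a discontinuation event dated on the day of Visit 4 itself, or an early termination visit treated as Visit 4.

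**2. Illustrate the size.** Only the 216 patients starting the assessment period come from the documents (SAP 4.1). The stop rates and the roughly even split at Visit 3 are assumptions.

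Middle scenario:

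- Stops for an AE up to Visit 3: 0.05 × 216 = 10.8, taken as 11. Remaining: 216 − 11 = 205, split 103 on 30/5 mg and 102 on 30/10 mg.
- Later AE stops at 3%: about 3 in each group.
- As written, 30/5 mg: 0/(103 − 3) = 0/100. 30/10 mg: 3/102 = 2.9%.
- Never up-titrated, 30/5 mg: (11 + 3)/(11 + 103) = 14/114 = 12.3%.
- Same 14 patients over everyone exposed to 30/5 mg: 14/216 = 6.5%.
- In neither dose column: 14 of the 17 patients who discontinue.

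| Assumed AE stops (up to Visit 3 / later) | 30/5 mg as written | Never up-titrated | Over all 216 starters | In neither dose column |
|---|---|---|---|---|
| 3% / 2% | 0/103 | 8/111 = 7.2% | 8/216 = 3.7% | 8 of 10 |
| 5% / 3% | 0/100 | 14/114 = 12.3% | 14/216 = 6.5% | 14 of 17 |
| 8% / 5% | 0/95 | 22/117 = 18.8% | 22/216 = 10.2% | 22 of 27 |

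A wider grid (stop rate *d* of 2% to 10% in each four-week interval, up-titrated fraction *u* of 30% to 70%) uses C = 216(1 − d)(1 − u) for patients continuing on 30/5 mg. The as-written count is 0 throughout. The never-up-titrated rate, (216d + dC)/(216d + C), runs from 4.8% to 34.3%, and 65% to 86% of discontinuations for an AE fall in neither dose column.

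The zero follows from the wording and does not depend on the assumed rates. The alternative percentages depend on both the rates and the choice of denominator.

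**The case against.** The strongest reply is that the duration phrase was meant only as a contrast with up-titrated patients, so that it means on 30/5 mg throughout and never moved to 30/10 mg. The sentence closes a passage about where up-titrated patients go, and 5.5 has no completion condition. Shell Table 14.1.1 supports this reading. Its 30/5 mg column has cells for exclusion at Visit 3 (blank under 30/10 mg), for adverse events and for death, and a row for completing combined therapy that would carry no information if only completers were admitted. The shell note about patients in neither group sits under that table too, so the note alone does not prove that early stoppers belong nowhere.

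Much of this stands. A reader might infer from 8.2 that the 30/5 mg discontinuation count is fixed at zero, or that these events drop out of the report. The documents do not support either as a settled result. A programmer working from Table 14.1.1 would not get zero, and every combined-period TEAE is in All Patients. The by-patient listings show whether an event led to discontinuation (16.2.7.2) and the regimen dates (16.2.5.2). The AE tables are also descriptive, with no planned dose comparison.

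The reply does not remove the conflict, for three reasons:

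- 5.5 is silent on early stoppers and yields to a more specific rule, which 8.2 supplies and 6.5 repeats.
- Table 14.1.1 is imperfect evidence, because its 30/5 mg column also has a cell for patients excluded at Visit 2, who never took the combination.
- All Patients cannot stand in for the 30/5 mg group. It is the Safety Population, which includes 30/10 mg patients and patients with no combination dose. The AE listings show the period but not the regimen, so attributing an event to 30/5 mg needs a link to the exposure listing.

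**Conclusion.** The point holds as a conflict in the column definition. On the literal reading of SAP 8.2, early stoppers on 30/5 mg are in neither dose column and the 30/5 mg count of discontinuation TEAEs is essentially zero, while early stoppers on 30/10 mg are counted. Table 14.1.1 points to a different intent, and two programmers could build different 30/5 mg columns from the same plan.

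Only the by-dose display is affected, in the AE tables and, through 6.5, the medication tables. The primary analysis is untouched.

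The percentages are illustrations on assumed stop rates. A reader might take 12.3% as the true 30/5 mg discontinuation rate that the table hides. It is not: its denominator leaves out the 102 up-titrated patients who also took 30/5 mg for four weeks, and over all starters the same 14 patients are 6.5%. The change should be made before database lock, but it is a correction to a secondary safety display.

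**What to change.** 1. In SAP 5.5, 6.5, 8.2 and the shell notes, use one definition of the 30/5 mg column: Safety Population patients with at least one dose of the 30/5 mg combination who never took 30/10 mg, whether or not they completed. Use that group as the denominator.
2. Keep patients with no combination dose in All Patients only, and reconcile the 30/5 mg cell for Visit 2 exclusions in Table 14.1.1 with that rule.
3. Correct the column label in 8.2 to ZOF/AML 30/5 mg.
4. Footnote the drawback of the new definition. All stops up to Visit 3 fall in the 30/5 mg column, and 30/10 mg patients have by definition stayed on 30/5 mg to Visit 3, so the two columns are not a fair dose comparison.
5. Because of that drawback, also report discontinuation AEs up to Visit 3 over all patients who started 30/5 mg (11/216 = 5.1% in the middle illustration).

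The cost is a sentence in three SAP sections, a revised programming note, one label and one extra summary line. No new data are needed.

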### 8.3 Clinical Laboratory Evaluations

For laboratory safety continuous variables, values recorded as "<X" or " $\leq$ X" or " $\geq$ Y" or " $\geq$ Y" will be imputed by "X" and "Y" respectively for descriptive statistics. This will be documented in a footnote in all output where such a replacement was performed. Continuous clinical laboratory observed values and change from Baseline (Visit 1) to Visit 4 will be summarized by combined therapy group (ZOF/AML 30/5 mg or ZOF/AML 30/10 mg) and overall for the SAF population.

Each laboratory result will be classified as Normal, Abnormal Not Clinically Significant (NCS), or Abnormal Clinically Significant (CS) at each visit. Shift tables from Baseline (Visit 1) to Visit 4 will be provided for each laboratory parameter, summarized by combined therapy group (ZOF/AML 30/5 mg or ZOF/AML 30/10 mg) and overall for the SAF population. If a patient has a missing lab parameter value at Visit 1 or Visit 4, that patient will be excluded from the shift analysis for that lab parameter but will be included in the corresponding by-patient data listing.

All laboratory parameters will also be presented in by-patient data listings for the SAF population.

Test	Visit	Laboratory Parameters to be Analyzed
		Red blood cell
		White blood cell
		Haemoglobin
		Haematocrit
		Platelets
		Neutrophils
		Lymphocytes
Haematology	Screening (Visit 1) and Visit 4	Monocytes
		Eosinophils
		Basophils
		Neutrophils absolute
		Lymphocytes absolute
		Monocytes absolute
		Eosinophils absolute
		Basophils absolute
		ALT
		Albumin
		Alkaline phosphatase
		AST
		Direct bilirubin
		Total bilirubin
		Total protein
		Creatinine
		Blood urea nitrogen
Serum Chemistry	Screening (Visit 1) and Visit 4	Creatine kinase
		GGT
		Triglycerides
		Cholesterol
		High- and low-density lipoprotein
		Chloride
		eGFR
		Blood glucose
		Potassium
		Uric acid

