FORM-000050125	2.0, CURRENT	Effective	08, Jan 2021

The patient must rest in a supine position for 5 minutes before the ECG is obtained. ECG tracings (paper or electronic) should be reviewed and interpreted by the Investigator or a qualified clinician. ECG parameters including ventricular rate, RR-Interval [ms], PR-Interval [ms], Rhythm (sinusal - other), PR, QRS, QT, QTcF, and QTcB intervals will be recorded.

If QTcF > 450 ms, it should be evaluated and used for clinical decision: another triplicate ECG is indicated and if required should be discussed with the Sponsor and/or medical monitor.

The original ECGs must be appropriately signed, collected and archived at the study site. Printouts and related copies for each ECG will include date, time, initials of the technician/nurse, and initials of the Investigator who reviewed the printout and should be properly archived at site.

Clinically relevant abnormalities should be recorded first on the source documents by the PI and then on the relevant section of the eCRFs.

Laboratory tests

A local laboratory will be used for laboratory evaluation. Clinical laboratory tests (chemistry and haematology) will be conducted at Screening (Visit 1) and Visit 4. Blood and urine samples for pregnancy test will be collected, processed, and analysed locally and in accordance to the research site's SOPs.

The maximum volume of blood to be taken is approximately 40 mL, which will be the total blood collected during the study.

The results should be evaluated for criteria defining AE and reported as such if the criteria are met. In all cases, the investigator must document in the source documents, the clinical considerations (i.e. results were or was not was clinically significant and/or medically relevant) in allowing or disallowing the patient to continue in the study.

To ensure patient safety, the patients will be contacted over phone within 24 hours, in case of any abnormality and clinically relevant laboratory test according to the Investigator's judgement at any visit. The results of laboratory tests will be returned to the Investigator, who is responsible for

MENARINI	Corporate Medical Department		
Identification Number	Version Number	State	Effective date
FORM-000050125	2.0, CURRENT	Effective	08, Jan 2021

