- Patients with abnormal renal function (creatinine clearance <30 mL/min) and/or abnormal liver enzyme parameters (alanine aminotransferase [ALT] or aspartate aminotransferase [AST] level of >2.5 × upper limit of normal [ULN] or total bilirubin level >1.5 × ULN).

If a patient has been withdrawn due to an AE, the Investigator must immediately contact the relevant pharmacovigilance contact (see Safety Data Management section). The reason for patient withdrawal must be well-documented in the Electronic Case Report Form (eCRF). The eCRF should capture the date and specific underlying reason for discontinuation of study product or patient discontinuation/withdrawal. Study treatment must be discontinued, and no further assessment conducted, and the data that would have been collected at subsequent visit will be considered missing. Further attempts to contact the patient are not allowed unless safety findings require communication or follow-up. All effort should be made to complete the assessment prior to study withdrawal. A final evaluation at the time of the patient's study withdrawal should be made as detailed in Early termination visit scheduled assessment.

Patients who discontinue from the study early will complete an early termination visit.

MENARINI	Corporate Medical Department		
	** * ** *	G	77.00 dt 1
Identification Number	Version Number	State	Effective date
FORM-000050125	2.0, CURRENT	Effective	08, Jan 2021

Subjects who prematurely withdrawn from study medication or from the study will not be replaced. These subjects will not be considered lost to follow-up.

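### If a local laboratory reports eGFR with an upper limit, the SAP 8.3 substitution rule shrinks the Visit 1 to Visit 4 eGFR change towards zero (minor; one descriptive safety row)

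*SAP*

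**What the plan says.** SAP 8.3 (Clinical Laboratory Evaluations) deals with continuous laboratory results that carry a limit sign. They "will be imputed by 'X' and 'Y' respectively for descriptive statistics", so the limit itself enters the table. The rule comes with disclosure: "This will be documented in a footnote in all output where such a replacement was performed".

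The same section then plans the summary: "Continuous clinical laboratory observed values and change from Baseline (Visit 1) to Visit 4 will be summarized by combined therapy group". Its parameter table lists both eGFR and creatinine under serum chemistry. The output is Table 14.3.4.1.2, backed by Listing 16.2.8.2. Two further displays are planned: "Shift tables from Baseline (Visit 1) to Visit 4 will be provided for each laboratory parameter", and "All laboratory parameters will also be presented in by-patient data listings for the SAF population".

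Protocol 8.2 says "A local laboratory will be used for laboratory evaluation", and that chemistry and haematology "will be conducted at Screening (Visit 1) and Visit 4". SAP 5.8 expects about 31 study centres. Neither document gives an eGFR equation, unit or reporting range, the number of laboratories, or a rule for a change computed from one or two censored values.

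**The concern.** Replacing an upper-censored result by its limit treats a bound as a measurement. For a single-visit mean this is a familiar convenience. For a change between two visits it has a direction: two results reported only as at or above the same limit give a difference of 0, however far apart the true values are.

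eGFR is the listed parameter where this deserves a check. Inclusion criterion 1 limits age to 65 or under, and exclusion criterion 6 removes patients with clinical evidence of renal disease, so many true values could lie above an upper reporting limit if one exists. Laboratory tests are a variable of safety Endpoint 2.5. Because blood is scheduled only at Visits 1 and 4, this is the only planned eGFR contrast. Where true renal function falls on average, the error runs towards showing no change. If laboratories used different limits, or some used none, one mean would also pool values that are not comparable.

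**Working it through.** The plan states no figure on this point, so there is none to reproduce. The check is arithmetic on the rule, followed by an illustration on assumed inputs.

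**Rule.** For an upper limit c:

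- recorded change = min(V4, c) − min(V1, c)
- true change = V4 − V1

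For a patient whose eGFR falls, there are three cases:

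- Both values at or above c: recorded change is 0.
- V1 at or above c and V4 below it: recorded change is V4 − c. The fall appears, but is too small by V1 − c.
- Both below c: recorded change equals true change.

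**Single-patient examples** (all values assumed):

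| V1 | V4 | True change | Recorded, c = 60 | Recorded, c = 90 | Recorded, c = 120 |
|---|---|---|---|---|---|
| 110 | 95 | −15 | 0 | 0 | −15 |
| 110 | 80 | −30 | 0 | −10 | −30 |
| 110 | 50 | −60 | −10 | −40 | −60 |
| 85 | 70 | −15 | 0 | −15 | −15 |

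**Group mean.** None of these inputs is in the documents: baseline mean 92 and SD 15; true change −5 with SD 9, independent of baseline; normal distributions; every patient at a laboratory with the same limit c. Then V4 has mean 92 − 5 = 87 and SD √(15² + 9²) = √306 = 17.49.

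For a normal variable with mean μ and SD σ, and with k = (c − μ)/σ,

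E[min(V, c)] = c − [(c − μ)Φ(k) + σφ(k)].

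- c = 60: 59.91 at Visit 1 and 59.54 at Visit 4; recorded mean change about −0.4.
- c = 90: 84.96 at Visit 1 and 81.42 at Visit 4; 81.42 − 84.96 = −3.54.
- c = 120: 91.82 at Visit 1 and 86.80 at Visit 4; 86.80 − 91.82 = −5.02.
- No limit: −5.

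A simulation of 2 million patients on the same inputs agrees with these means. It also shows that 79% of true falls of 15 or more are recorded as 0 at c = 60, and 13% at c = 90.

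**Sensitivity.** With c = 60, a baseline of 85 (SD 16) gives −0.9 and a baseline of 98 (SD 14) gives −0.1, against a true −5. If half the patients attend laboratories with a limit of 60 and the rest have none, the recorded change is about (−0.4 − 5.0)/2 = −2.7.

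**The case against.** The strongest reply is that the trigger is not in the documents. Neither says that any laboratory reports eGFR with an upper limit. If none does, or if the limits are as high as 120, the rule does no measurable harm. That stands, and it makes the point conditional. The eGFR distribution used above is assumed as well.

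Three stronger readings are tempting, and the documents do not support them.

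- A reader might infer that the table will show no change whenever renal function falls. That is so only when both values are at or above the limit. A fall through the limit is shown, though understated, and a fall wholly below it is shown in full.
- A reader might link the rule to the withdrawal criterion in Protocol 10 ("Patients with abnormal renal function (creatinine clearance <30 mL/min"). That criterion is applied to individual patients on creatinine clearance and does not use the summarised eGFR.
- A reader might count 31 laboratories. SAP 5.8 gives study centres, not laboratories.

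It can also be said that the information is lost in the laboratory's report, before the SAP rule applies, and that safeguards exist. Both are fair. The replacement is confined to descriptive statistics and footnoted. Creatinine, a measured quantity that an eGFR limit does not censor, is summarised at the same two visits. Clinically relevant abnormalities are managed as adverse events (Protocol 9.9), and the CRO and sponsor review out-of-range values every two months (Protocol 9.12).

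The safeguards are not complete. SAP 8.3 requires the footnote to say that a replacement was made, but not how many values were replaced or how many changes involve one. The shift table and listing add little when both results carry the same limit. And although the laboratory does the censoring, the substitution is what turns a bound into an apparently exact change.

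**Conclusion.** The point holds in conditional form and is minor. If eGFR is reported with an upper limit that many patients exceed, the mean change in Table 14.3.4.1.2 is biased towards zero. On the assumed inputs a true −5 becomes about −0.4 with a limit of 60 and −3.5 with a limit of 90, and stays at −5.0 with a limit of 120 or none. The size rests wholly on assumed limits and an assumed eGFR distribution; only the rule and its direction come from the documents.

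The effect is confined to the eGFR row of one descriptive safety table. The creatinine row, the creatinine-clearance withdrawal rule and the primary analysis are unaffected. In practice, the eGFR and creatinine rows could tell different stories, and a reader of the table could not tell from the eGFR row why.

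**What to change.** In SAP 8.3, before database lock:

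1. Exempt eGFR from the replacement rule and keep the rule for the other parameters.
2. Derive eGFR at Visit 1 and Visit 4 from the recorded creatinine (converted to one unit), age and sex, with one equation named in the SAP.
3. Use the derived value in Table 14.3.4.1.2, and keep the laboratory-reported eGFR in Listing 16.2.8.2.

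This removes the dependence on any laboratory's reporting limit and makes the formula the same at every site. It needs no new data, because creatinine is in the chemistry panel and age and sex are in the demographic record. The cost is one SAP amendment and one derived variable with unit conversion. The downside is that derived values may differ from those on the laboratory reports, which a footnote should state.

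If the sponsor prefers to tabulate the laboratory value, the least that would serve is to report the number of censored eGFR values at each visit, flag changes that involve one, and read renal change from the creatinine row.
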